12.5 Abnormal Vital Sign Values

Not every vital sign abnormality qualifies as an adverse event. A vital sign result must be reported as an adverse event if it meets any of the following criteria:

- Is accompanied by clinical symptoms
- Results in a change in study treatment (e.g., dosage modification, treatment interruption, or treatment discontinuation)
- Results in a medical intervention (e.g., potassium supplementation for hypokalemia)
- Is clinically significant in the investigator's judgment
- Requires a change in concomitant therapy (i.e. addition of, interruption of, discontinuation of, or any other change in a concomitant medication, therapy or treatment)

It is the investigator's responsibility to review all vital sign findings. Medical and scientific judgment should be exercised in deciding whether an isolated vital sign abnormality should be classified as an adverse event.

If a clinically significant vital sign abnormality is a sign of a disease or syndrome (e.g., high blood pressure), only the diagnosis (i.e., hypertension) should be recorded on the Adverse Event CRF.

Observations of the same clinically significant vital sign abnormality from visit to visit should not be repeatedly recorded on the Adverse Event CRF, unless the etiology changes. The initial severity of the event should be recorded, and the severity or seriousness should be updated any time the event worsens.

12.6 Clinical Safety Laboratory Assessments

Clinical laboratory tests will be performed at specified in the [3.2 Schedule of Activities](#). (Refer to [section 26.0](#): for the list of clinical laboratory tests).

The investigator must review the laboratory report, document this review, and record any clinically relevant changes occurring during the study in the AE section of the CRF. The laboratory reports must be filed with the source documents.

Protocol for clinical study of Brequinar

Protocol No.: 21-VIN-0372

Version No.: 2.1; Dated: 29 Dec 2021

Supersedes: 02; Date of Supersedes: 30 Sep 2021

All laboratory tests with values considered clinically significantly abnormal during the study or within 30 days after the last dose of study intervention should be documented as AE. The abnormal test should be repeated until the values return to normal or baseline or are no longer considered clinically significant.

- If such values do not return to normal/baseline within a period of time judged reasonable by the investigator, the etiology should be identified and the sponsor notified.
- If laboratory values from non-protocol specified laboratory assessments performed at the institution's local laboratory require a change in participant management or are considered clinically significant by the investigator (e.g., SAE or AE or dose modification), then the results must be recorded in the CRF.

12.7 Other safety evaluations as appropriate and as indicated in the schedule of activities

- Pregnancy test (Serum and Urine): At specified in the [3.2 Schedule of Activities](#).

12.8 Abnormal Laboratory Values

Not every laboratory abnormality qualifies as an adverse event. A laboratory test result should be reported as an adverse event if it meets any of the following criteria:

- Is accompanied by clinical symptoms
- Results in a change in study treatment (e.g., dosage modification, treatment interruption, or treatment discontinuation)
- Results in a medical intervention (e.g., potassium supplementation for hypokalemia)
- Is clinically significant in the investigator's judgment
- Requiring a change in concomitant therapy (i.e. addition of, interruption of, discontinuation of, or any other change in a concomitant medication, therapy or treatment)

It is the responsibility of the investigator to review all laboratory findings. Medical and scientific judgment should be exercised in deciding whether an isolated laboratory abnormality should be classified as an adverse event. The investigator must review the laboratory report, document this review, and record any clinically relevant changes occurring during the study in the AE section of the CRF.

If a clinically significant laboratory abnormality is a sign of a disease or syndrome (e.g., alkaline phosphatase and bilirubin 5 × ULN associated with cholecystitis), only the diagnosis (i.e., cholecystitis) should be recorded on the adverse event CRF.

If a clinically significant laboratory abnormality is not a sign of a disease or syndrome, the abnormality itself should be recorded on the adverse event CRF, along with a descriptor indicating if the test result is above or below the normal range (e.g., "elevated potassium," as opposed to "abnormal potassium").

Observations of the same clinically significant laboratory abnormality from visit to visit should not be repeatedly recorded on the adverse event CRF, unless the etiology changes. The initial severity of the event should be recorded, and the severity or seriousness should be updated any time the event worsens.

Protocol for clinical study of Brequinar

Protocol No.: 21-VIN-0372

Version No.: 2.1; Dated: 29 Dec 2021

Supersedes: 02; Date of Supersedes: 30 Sep 2021

For each laboratory abnormality reported as an AE, the following laboratory values should be reported in the laboratory section of the CRF: the value indicative of the onset of each toxicity grade; the most abnormal value observed during the AE, and the value supporting recovery to Grade ≤ 1 or to baseline values. The CTCAE version 5 scale will be used to grade AEs including laboratory AEs.

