5.5 Adverse Reactions

Brequinar:

As discussed above, brequinar is an investigational drug that has been given to 71 patients with COVID-19. Adverse events related to brequinar were mild to moderate and infrequent, and no subjects discontinued brequinar treatment due to a related adverse event in either of the two COVID-19 studies.

Brequinar has also been given to more than 800 patients with various forms of cancer in more than 20 clinical trials and has also been tested in patients with psoriasis and those who have had a kidney or liver transplant. The most common side effects in cancer patients when given higher doses of brequinar have been:

- Thrombocytopenia, which may require replacement. Low platelet count can lead to bruising, nose bleeds, vomiting blood, bloody diarrhea, blood in the urine, bloody gums, coughing up blood, and taking longer to stop bleeding from cuts.
- Stomatitis/mucositis.
- Other risks associated with brequinar include:
 - Skin rash,
 - Nausea,
 - Vomiting,
 - Diarrhea,
 - Leukopenia,
 - Anemia,
 - Yellowing of the skin or whites of the eyes caused by high levels of the pigment bilirubin,
 - Abnormal liver tests,
 - Abnormal kidney function,
 - Cardiac complications, and
 - Fatigue

Some of these side effects were severe enough in patients treated with brequinar to require hospitalization or caused death. In most cases, these side effects went away within about 2 weeks after patients stopped taking brequinar.

Patients must be contact to study doctor/study staff if they experience any of the following:

- Discoloration/bruising of the skin or a rash of red/purple spots on your skin. These can be caused by bleeding in or under the skin,
- Nose bleed,
- Coughing up blood,

Protocol for clinical study of Brequinar

Protocol No.: 21-VIN-0372

Version No.: 2.1; Dated: 29 Dec 2021

Supersedes: 02; Date of Supersedes: 30 Sep 2021

- Blood in urine,
- Bleeding gums,
- Prolonged bleeding time from needle sticks, abrasions or lacerations,
- Vomiting blood,
- Rectal bleeding,
- Blood in stool,
- Any other unusual bleeding

Dipyridamole:

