7.0 STUDY ENDPOINTS

Primary Endpoints:

- Frequencies of grade 3 and 4 toxicities and serious adverse events (SAEs) considered by the investigator to be related to the combination, brequinar alone or placebo alone.

Secondary Endpoints:

- qPCR SARS-CoV-2 levels through Day 29 and at days 4, 8, 12, 15, 22, and 29;
- Time to symptom improvement through Day 29;
- Percentage of subjects requiring hospital admission/re-admission as an in-patient for >24 hours through Day 29;
- Percentage of subjects requiring medical attended visits, e.g., hospitalization, emergency room visits, Urgent Care/Family Doctor visits through Day 29;
- Percentage of subjects requiring supplemental support such as oxygen through Day 29.

Exploratory Endpoints (PK):

- Analysis of brequinar's pharmacokinetic profile in a subset of patients that have received brequinar as a part of therapy and have consented to provide PK samples.

Clinical improvement will be defined as a 2-point or greater improvement on an 8-point WHO ordinal scale in every subject measured on each designated day, from the date of randomization through day 29. This scale has been used in the current COVID-19 outbreak.

Ordinal Scale for Clinical Improvement

Patient State	Descriptor	Score
Uninfected	No clinical or virological evidence of infection	0
Ambulatory	No limitation of activities	1
	Limitation of activities	2
Hospitalized	Hospitalized, no oxygen therapy	3

Protocol for clinical study of Brequinar

Protocol No.: 21-VIN-0372

Version No.: 2.1; Dated: 29 Dec 2021

Supersedes: 02; Date of Supersedes: 30 Sep 2021

Mild disease	Oxygen by mask or nasal prongs	4
Hospitalized	Non-invasive ventilation or high-flow oxygen	5
Severe Disease	Intubation and mechanical ventilation	6
	Ventilation + additional organ support – pressors, RRT, ECMO	7
Dead	Death	8

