9.11 Clinical Safety Measures

It is the responsibility of the investigator to ensure that adequate medical supervision and care is available for the study subjects during the study to ensure their utmost safety and well being.

- Demography (subject reported / measured height and weight, age, sex and race/ethnicity): At screening
- Medical history (relevant within 30 days or ongoing) / History of current illness (date of symptom onset or change in baseline co-morbidity thought to be due to COVID-19 infection): At screening
- Physical Examination (subject self-reported / examiner evaluated): At screening
- Vital signs (body temperature, respiratory rate, heart rate, SpO₂) assessment: At screening, Day 4 (± 8 hrs), Day 8 (± 8 hrs), Day 12 (± 1 day), Day 15 (± 1 day), Day 22 (± 1 day), End of study [EoS; Day 29 (± 2 day)].

Note: If subject is hospitalized, Vital signs assessment will be done on daily basis by site team during hospitalization through Day 8 then following the Vital signs visits as listed above.

- Hematology, biochemistry and urine analysis: At screening, Day 1 unless same day as Screening visit, Day 8 (± 8 hrs), Day 15 (± 1 day), End of study [EoS; Day 29 (± 2 day)].

- HCV, HbSAg, HIV Test: At screening

- Serum pregnancy test (Women of child bearing potential (WOCBP)): At screening.

- Urine pregnancy test (WOCBP): End of study [EoS; Day 29 (± 2 day)].

Note: WOCBP: A premenopausal female capable of becoming pregnant

- Rapid antigen test / SARS-CoV-2 RT-PCR Qualitative (in a clinically relevant specimen (Naso-Oro-

Protocol for clinical study of Brequinar

Protocol No.: 21-VIN-0372

Version No.: 2.1; Dated: 29 Dec 2021

Supersedes: 02; Date of Supersedes: 30 Sep 2021

Pharyngeal as appropriate)): Screening

Note: Test need not be repeated in those with possession of confirmed positive report. Date of positive report must be \leq 5 days prior to randomization.

- RT-PCR Quantitative Viral (in a clinically relevant specimen (Naso-Oro-Pharyngeal as appropriate)): Day 1 (Prior to dosing), Day 4 (\pm 8 hrs), Day 8 (\pm 8 hrs), Day 12 (\pm 1 day), Day 15 (\pm 1 day), Day 22 (\pm 1 day) and End of study [EoS; Day 29 (\pm 2 day)]
- Ordinal Scale Assessment: Screening, Day 8 (\pm 8 hrs), Day 15 (\pm 1 day), Day 22 (\pm 1 day) and End of study [EoS; Day 29 (\pm 2 day)]

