12.9 Handling and Reporting of Adverse Events

An adverse event is any untoward medical occurrence (including a symptom or disease or an abnormal laboratory finding) during treatment with an investigational drug or a pharmaceutical product in a subject that does not necessarily have a relationship with the treatment being given.

*Abnormalities based on laboratory parameters, vital signs, and 12-Lead ECG will be called AE, if they are associated with at least one of the following:

- Interruption or stoppage of the study medication
- Associated with signs or symptoms
- Requiring treatment
- Considered clinically significant by the investigator

Safety Criteria:

An independent, unblinded study physician (from CRO) will assess each cohort for safety. A cohort will be declared safe as soon as all results are available for the Day 15 visit if the following conditions are met:

- No toxic deaths (deaths judged by the investigator to be related to either study drug);
- Not more than 1 toxic SAE (SAEs judged by the investigator to be related to either study drug);
- No Grade 3 or higher toxicities (including laboratory AEs as per CTCAE version 5.0 or higher) (AEs judged by the investigator to be related to either study drug);
- <4 subjects with any grade toxicity (AEs judged by the investigator to be related to either study drug).

In addition to the cohort-level safety, the independent study physician (from CRO) will determine if any subjects meet Individual Stopping Criteria:

- Subjects who develop a Grade 3 toxicity that is assessed by the investigator to be related to the study drug are to be permanently discontinued from study treatment but will continue in the study for safety assessments.
- Subjects who develop a Grade 4 toxicity, regardless of relatedness to study drug, are to be permanently discontinued from study treatment but will continue in the study for safety assessments.

In addition to the individual subject-level safety, the independent study physician (from CRO) will determine if a cohort meets Cohort-level Stopping Criteria prior to completing the 16 subjects, in which case no additional subjects will be enrolled into that cohort and no higher brequinar doses will be assessed:

Protocol for clinical study of Brequinar

Protocol No.: 21-VIN-0372

Version No.: 2.1; Dated: 29 Dec 2021

Supersedes: 02; Date of Supersedes: 30 Sep 2021

- ≥ 3 brequinar-treated or combination-treated subjects meet the individual stopping criteria.

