15.4 Analysis of Efficacy Data

All statistical analysis will be done using SAS® Version 9.4 or higher (SAS Institute Inc., USA).

For continuous variables, the summary statistics will be the number of observations, mean, standard deviation, median, minimum and maximum values. Categorical values will be summarized using frequencies and percentages.

Primary Endpoints:

- Frequencies of grade 3 and 4 toxicities and serious adverse events (SAEs) considered by the investigator to be related to the combination, brequinar alone or placebo alone.

Because the primary study endpoint is a safety parameter no formal statistical testing will be performed for this parameter.

Protocol for clinical study of Brequinar
 Protocol No.: 21-VIN-0372
 Version No.: 2.1; Dated: 29 Dec 2021
 Supersedes: 02; Date of Supersedes: 30 Sep 2021

Secondary Endpoints:

For subjects treated with the brequinar-dipyridamole combination compared to subjects treated with the brequinar and to subjects treated with the placebo combination through Day 29, to determine:

- SARS-CoV-2 levels through Day 29 and at days 4, 8, 12, 15, 22, and 29 will be analyzed using analysis of covariance (ANCOVA) test;
- Time to symptom improvement through Day 29 will be analyzed using Kaplan-Meier time-to-event analysis;
- Percentage of subjects requiring hospital admission/re-admission as an in-patient for >24 hours through Day 29 will be analyzed using Fisher exact / chi square test;
- Percentage of subjects requiring medical attended visits, e.g., hospitalization, emergency room visits, Urgent Care/Family Doctor visits through Day 29 will be analyzed using Fisher exact / chi square test ;
- Percentage of subjects requiring supplemental support such as oxygen through Day 29 will be analyzed using Fisher exact / chi square test.

Exploratory Endpoints:

- Brequinar's pharmacokinetic profile in a subset of patients that have received brequinar as a part of therapy and have consented to provide PK samples will be analyzed descriptively.

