15.5 Safety Analysis

All safety analysis will be conducted using the safety population set.

Frequency distribution or summary statistics of all demographics variable and baseline characteristics will be generated by treatment arm.

The evaluation of the drug safety will be based on clinical AEs, vital signs, physical examination, concomitant medications and laboratory abnormalities reported during the study and incidence of adverse events and treatment emergent adverse events in each arm during the study. All safety presentations will include subjects who receive at least one dose of the study medication and will group subjects by treatment received. Frequency distributions and individual listings of all adverse events will be generated. Changes in clinical laboratory test results from baseline will be listed.

A treatment emergent adverse event is defined as any event not present prior to the initiation of the treatments or any event already present that worsens in either intensity or frequency following exposure to the treatments.

Adverse events will be coded using Medical Dictionary for Regulatory Activities (MedDRA) terms using the version that is current at the time the first subjects is enrolled and will be summarized by system organ class (SOC) and preferred term within SOC. The Common Terminology Criteria for Adverse Events CTCAE 5.0 will be used to grade the severity of adverse events.

Protocol for clinical study of Brequinar

Protocol No.: 21-VIN-0372

Version No.: 2.1; Dated: 29 Dec 2021

Supersedes: 02; Date of Supersedes: 30 Sep 2021

Adverse Events will be summarized by treatment and overall. AE summary tables will include counts of subjects and the number of events. If a subject experiences more than one episode of a particular AE, that subject will be counted only once for that event. If a subject has more than one AE that coded to the same preferred term, the subject will be counted only once for that preferred term. Similarly, if a subject has more than one AE within a SOC, the subject will be counted only once in that SOC.

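### Grade 3 or 4 laboratory values can miss the primary safety count because grade alone does not make them adverse events; a programmed grade table beside the endpoint would show them

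*Combined protocol and SAP*

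**What the plan says.** All references are to protocol Version 2.1.

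- **Primary endpoint (Sections 7.0 and 15.4).** "Frequencies of grade 3 and 4 toxicities and serious adverse events (SAEs) considered by the investigator to be related to the combination". The same count is made in the other two arms. Section 7.0 does not define toxicity.
- **Cohort safety condition (Section 12.9 and synopsis).** "No Grade 3 or higher toxicities (including laboratory AEs as per CTCAE version 5.0 or higher". The events meant are AEs that the investigator attributes to one of the study drugs. Laboratory findings enter here as laboratory AEs, not as graded values.
- **From laboratory value to AE (Section 12.8).** "Not every laboratory abnormality qualifies as an adverse event". Five criteria follow: symptoms, a change in study treatment, a medical intervention, a change in concomitant therapy, or clinical significance in the investigator's judgment. Section 12.9 gives a shorter list of four, and Section 12.6 relies on values considered clinically significant. None of the three mentions CTCAE grade.
- **Grading (Sections 12.8 and 15.5).** CTCAE version 5 is applied to AEs, including laboratory AEs.
- **Schedule (Sections 9.11 and 10.1).** Dosing is on Days 1 to 5. "Hematology, biochemistry and urine analysis: At screening, Day 1 unless same day as Screening visit, Day 8". Further tests follow on Days 15 and 29.
- **Other laboratory reporting.** Section 15.5: "Changes in clinical laboratory test results from baseline will be listed". The synopsis adds descriptive summaries. Neither specifies a table by grade.
- **Known risk (Section 5.5).** The common side effects of brequinar in cancer patients at higher doses begin with "Thrombocytopenia, which may require replacement". The section also names a raised risk of thrombocytopenia with dipyridamole, and says the combination has not been tested clinically before.

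**The concern.** A CTCAE laboratory grade for a platelet count can be read from the value itself, and the samples go to a central laboratory. The plan could therefore count these events uniformly across sites, arms and cohorts. Instead a value must first be reported as an AE and then be judged related before it reaches the primary endpoint. For an asymptomatic value that needs no treatment, the first step rests on one investigator's view of clinical significance.

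Two results depend on that step: the primary frequencies, and the cohort condition that allows no related Grade 3 or higher toxicity. If sites differ in what they report, the counts can differ between cohorts for reasons unrelated to dose, and no specified table would let a reader see it.

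**Working it through.** The plan gives no event rate, power or precision figure for the primary endpoint, so there is nothing of its own to reproduce. The check has two parts.

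**1. Tracing one case through the text.** Take a subject with an asymptomatic Grade 3 platelet count at the Day 8 visit who needs no treatment.

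| 12.8 criterion | Met? |
|---|---|
| Symptoms | No, by assumption |
| Change in study treatment | No: the last dose was on Day 5, and the Day 8 window is ±8 hours |
| Medical intervention | No, by assumption |
| Change in concomitant therapy | No, by assumption |
| Clinically significant in the investigator's judgment | Only if the investigator says so |

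The four criteria in 12.9 lead to the same place. If the answer in the last row is yes, the event must still be judged related. An unscheduled test during Days 1 to 5 is allowed under 9.11 and could lead to a change in study treatment, but the schedule does not call for one.

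**2. Sizing the possible effect.** Inputs:

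- n = 12 active subjects per Part 1 cohort (8 combination + 4 brequinar alone, Section 9.1).
- p = true rate of related Grade 3 or higher laboratory events. This is an assumption, taken as 2%, 5% and 10%; the documents give no rate.
- q = share of those events reported as AEs and counted. This is also an assumption: 1 (full capture) or 0.5 (half).

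The chance that a cohort shows no counted event is (1 − p·q)^12, taking subjects as independent.

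| p | Full capture | Half capture |
|---|---|---|
| 2% | 0.98^12 = 78% | 0.99^12 = 89% |
| 5% | 0.95^12 = 54% | 0.975^12 = 74% |
| 10% | 0.90^12 = 28% | 0.95^12 = 54% |

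These are also the chances, as far as laboratory events go, that a cohort meets the single condition of no related Grade 3 or higher toxicity. They are not the chances of being declared safe, because other conditions apply as well.

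At the expanded dose there are 8 + 32 = 40 combination subjects. The expected count at p = 10% is 40 × 0.10 = 4.0 with full capture and 40 × 0.05 = 2.0 with half. At p = 5% it is 2.0 and 1.0.

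**The case against.** The strongest case against is that the remaining route is not a loose one. Section 12.12 describes Grade 3 as severe or medically significant and Grade 4 as life-threatening, so an investigator who recognises such a grade has nearly conceded clinical significance. Section 12.6 requires every laboratory report to be reviewed and the review documented, and 12.9 opens with an AE definition that includes abnormal laboratory findings. There are further layers: an unblinded CRO physician assesses each cohort once Day 15 results are in, the DSMB meets before the expansion, and regulators must approve the Part 1 safety data first. The values remain in listings and summaries. The study is descriptive and does not test the primary endpoint.

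Most of this stands, and it limits the point. It makes wide under-reporting less likely, but no sentence makes a Grade 3 or 4 value an AE, and the cohort condition is worded in terms of investigator-judged AEs.

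A reader might go further in four ways that the documents do not support.

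- **The primary frequency is biased downward.** The text shows that values can be missed, not that they will be. Assessors are meant to be blinded to arm, and no between-arm distortion is shown.
- **Thrombocytopenia is the main expected toxicity.** Section 5.5 lists stomatitis/mucositis beside it, from cancer patients at higher doses. In the 71 COVID-19 patients, related events are described as mild to moderate and infrequent. Those data do not cover the combination.
- **No analysis will grade laboratory values.** A separate SAP with mock tables is promised and is not among these documents. It could define toxicity from graded values.
- **The primary endpoint should count all graded values.** That would replace an endpoint defined by relatedness. Causality is assessed for AEs, so a value never reported as one carries no relatedness judgment and could not be placed in a related-only count.

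**Conclusion.** The gap is real but limited. In Version 2.1 a Grade 3 or 4 laboratory value reaches the primary endpoint and the cohort condition only after it is reported as an AE and judged related, and grade alone does not trigger reporting. For an asymptomatic, untreated value found at a scheduled visit, counting depends on the investigator's judgment of clinical significance.

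The size cannot be established from the documents. Under the assumed rates, half capture raises the chance of an event-free cohort of 12 active subjects by about 10 percentage points at a 2% true rate (78.5% to 88.6%), 20 at 5% (54.0% to 73.8%) and 26 at 10% (28.2% to 54.0%). Both the true rate and the capture share are assumptions, and better capture would shrink these differences. The change is a cheap improvement in reporting and does not require a new primary endpoint.

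**What to change.** Keep the primary endpoint based on investigator-related AEs. Then:

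1. In Sections 15.4 and 15.5 and in the SAP, prespecify a supportive analysis shown beside the primary table. It should include every treatment-emergent central-laboratory value of CTCAE v5 Grade 3 or higher that is at least one grade worse than baseline, derived by program whether or not an AE was reported and regardless of relatedness. Present it by arm and dose, with a flag for whether an AE was recorded.
2. Replace the listing-only statement in 15.5 with a shift table from baseline grade to worst post-baseline grade.
3. Reconcile 12.8, 12.9 and the laboratory wording in the safety criteria so that it is clear which laboratory values count. Which values should count in the clinical rules is for the sponsor to settle.

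The cost is some wording and a little programming on data already collected, with no new visits or samples. The table may show a higher rate than the primary count and will include some changes due to COVID-19 itself. Placebo helps interpret those in Part 1 only, because the 48-subject expansion has no placebo arm.
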